2.1. Sample Size

We plan to enroll approximately 300 adolescent (age 13-18) and parent dyads who have an appointment with a participating provider affiliated with one of six participating practices in the Puget Sound Pediatric Research Network (PSPRN). We also plan to enroll approximately 30 PSPRN providers (about 5 providers per clinic).

2. Gender of Subjects

This study does not have any gender-based restrictions. However, given that women are more frequently primary caregivers and PCPs, we estimate the following gender distribution in our study population:

Adolescents: 150 Females and 150 Males

Caregivers: 240 Females and 60 Males

PCPs: 18 Females and 12 Males

3. Age of Subjects

Participants will include adult *caregivers and PCPs* (over the age of 18 years) and *adolescents* (age 13-18). As health risk behaviors typically begin in adolescence and persist into adulthood, we are targeting adolescents rather than children less than 13 years of age.

4. Racial and Ethnic Distribution

The proposed study population will include a wide cross section of adolescent patients and their caregivers, including many families of ethnoracial minority status. We will monitor diversity in our sample throughout the course of recruitment and adapt recruitment efforts as needed to assure a representative sample. The Central Puget Sound geographic area, where our study population is situated, consists of the following approximate ethnic and racial breakdown:

- 73% White
- 5% African American
- 12% Asian, Hawaiian or Other Pacific Islander
- 1% American Indian or Alaska Native
- 9% some other race (alone) or two or more races

In addition, 9% of individuals in this geographic area are of Hispanic or Latino ethnic background.

5. Inclusion Criteria

Eligible caregivers will have a child 13 to 18 years old who has an appointment with a participating provider at a PSPRN clinic and will be able to understand English.

Eligible adolescents will be 13 to 18 years old, have an appointment with a participating provider at a PSPRN clinic and will be able to understand English.

Eligible PCPs will include providers (i.e., pediatricians, family practitioners, physician assistants and nurse practitioners) affiliated with a PSPRN clinic who are following a panel of adolescent patients and will be able to understand English.

6. Exclusion Criteria

Caregivers will be excluded from the study if they do not speak English; or if their child is not eligible or declines to participate in the study.

Adolescents will be excluded from the study if they do not meet age requirements, do not have an appointment with a participating provider at a PSPRN clinic, lack the means to complete follow-up interviews (i.e., have neither telephone nor internet access), have a sibling who has been/is being enrolled in the study or have previously participated in our previous trial comparing Check Yourself to usual care, and/or are not able to understand English. Our experience in the Seattle region is that due to excellent English Language Learning school supports, inability to read or understand English is a barrier for <0.5% of adolescents. Thus, we do not anticipate that language restrictions will significantly limit the demographic distribution of our participants.

PCPs will be excluded from the study if they do not speak English, are not following a panel of adolescent patients, and are not affiliated with a participating PSPRN clinic.

7. Vulnerable Subjects

[figure not shown]
This study's focus is on adolescent health care, and adolescents are study participants. We plan to enroll 300 adolescent subjects aged 13-18. Most will be minors. Study activities for minor adolescents will be no different from study activities for 18-year-old adolescents. The risk/benefit ratio is the same for all adolescent participants regardless of age. Research staff will obtain oral consent from 18-year-old participants directly, without contacting a caregiver. For younger adolescents, research staff will first obtain oral parental consent before obtaining oral assent.

3. **Methods and Procedures**

3.1. Study Design

This study will evaluate the effect of I-ACT with Check Yourself on adolescent-perceived quality of care (i.e., satisfaction and perception of PCP communication), motivation for health, and health risk behaviors using a stepped wedge study design. The study will take place in 6 participating PSPRN affiliated clinics, where the system of interventions (I-ACT with Check Yourself) will be rolled-out sequentially to the clinics, chosen in random order, over spaced time intervals (see Figure 1). We refer to pre-implementation of I-ACT with Check Yourself, as the control period and post-implementation as the intervention (i.e., case) period.

Figure 1: Stepped Wedge Study Design and Timeline

We anticipate that approximately 30% of youth approached will participate in the study. Thus, we will invite approximately 1000 adolescent/caregiver dyads to participate in the study, in order to yield 300 adolescent/caregiver dyad participants in our total sample. Upon enrollment, caregiver participants will be asked to complete a brief (10-minute) web-based questionnaire about their education/occupation, their adolescent's health history, and an open-ended question about what they would like to get from PCPs for themselves and their adolescent. Adolescents who enroll in the study will receive either electronic health screening alone (i.e., control group) if

their clinic appointment occurs in the pre-I-ACT implementation period or Check Yourself (i.e., intervention group) if their clinic appointment occurs in the post-implementation period.

At baseline (T1), adolescents will be asked to complete a web-based screening survey that includes questions about guideline-recommended health risk behavior screening areas, including substance use, nutrition, physical activity, sexual behavior, depressive symptoms, and safety. The screener questions themselves are current standard of care. Adolescents will also be asked to report their age, gender, race/ethnicity, interest in discussing health risks with the PCP, and self-efficacy.

Adolescents in the control group will complete the web-based screening survey for research purposes, but neither they nor their PCP will receive feedback about their health behaviors. PCPs will screen and counsel the patient as they would normally do under usual care conditions, consistent with the current standard of care.

During the intervention period, participating PCPs will receive adolescent-centered communication training, based on the tenets of motivational interviewing, to reinforce healthy behavior choices and to engage youth and parents to reduce risk behaviors as appropriate. PCPs will also receive three feedback reports (baseline, 2 months and 4 months) on adolescent-reported receipt of counseling on each of the target behaviors and adolescent-reported visit satisfaction and follow-up care. PCPs will not be asked to complete any study questionnaires; all of the outcome data will be gathered directly from adolescents and caregivers. Outcome data for the three feedback reports will be given to providers in aggregate form and will be void of individual identifiers.

Adolescents in the intervention group will receive full personalized motivational feedback following completion of the screening survey, both with web-based delivery. Their PCPs will receive a summary report which will include specific information on the adolescent's responses that will allow them to reinforce healthy behavior choices and implement further brief, in-person interventions for moderate to high risk adolescents. The personalized feedback to the participant and provider is consistent with current standard of care. However, the electronic method of delivery is unique to this project.

In order to administer follow-up surveys, we will ask adolescents to provide an email address, cell phone number, or phone number. One day (T2) following their PCP appointment, adolescent participants will be asked via email, text message or phone to complete a survey about their motivation for health, perception of PCP communication, and experiences. Both adolescents and their caregivers will be asked about their satisfaction with treatment during the appointment with their PCP. In addition, caregivers will be asked open-ended questions to assess the provider's delivery of caregiver education regarding strategies to reduce health risks for their child during the visit.

Three (T3), six (T4) and twelve (T5) months following their PCP appointment, adolescent participants will be asked via email, text message or phone to complete all assessments

administered at T1 and T2 except the questionnaires related to delivery of preventive counseling, demographics, interest in discussing health risks with PCP, and self-efficacy. Additionally, adolescents will be asked about follow-up care they may have received. At T2 and T3, adolescent participants will be asked about their general satisfaction with their provider and will be asked 3-4 follow-up questions to ascertain satisfaction with the Check Yourself app and study. These surveys are not standard of care, because they are not collected as part of an appointment; however, the probability and magnitude of discomfort associated with the completion of these surveys is no greater than ordinarily encountered in daily life or during the performance of routine psychological examinations/tests or medical care.

3.2. Measures by Construct and Time point

Tables 1 and 2 describe the study measures by construct.

Table 1: Measures used in the study, organized by construct and method.

Measures and Constructs	Time point
Moderators	
Gender, age, race, household composition, school, truancy, support, goals, interest in discussing health risks with provider	T1(A)
Number of visits with provider	T2(A)
Health Self-Efficacy	T1(A), T2 (A), T3(A), T4(A), T5(A)
Caregiver Concerns	
Guidelines for Adolescent Preventative Services Caregiver Questionnaire: adolescent health risk behavior concerns.	T1(C)
Perception of provider engagement with the caregiver	T2 (C)
Intermediary Targets	
Health Motivation (Readiness to Change Rulers): Self-report used to assess adolescent motivation for change among specific health behaviors.	T1(A), T2 (A), T3(A), T4(A), T5(A)
Adolescent Report of the Visit: adolescent-report of the PCPs' delivery of risk behavior screening and counseling based on risk level.	T2 (A)
Interval Receipt of Care: adolescent self-report of extent of follow up care.	T3 (A), T4(A), T5(A)
Main Outcomes: Satisfaction & Perception of PCP Communication	

Satisfaction Questionnaire: self-report of satisfaction with care based on items adapted from the Consumer Assessment of Healthcare Providers and Systems (CAHPS) measure.	T2(A/C)
Adolescent Perception of Patient-Centeredness: adolescent self-report of how adolescents feel about visits with their primary caregiver.	T2(A)
Main Outcomes: Health Risk Dimensions*	
Alcohol Consumption and Marijuana Use: self-report based on items about typical quantity and frequency of drinking, smoking/using tobacco, and marijuana use (each calculated separately) over the past 30 days.	T1(A), T3(A), T4(A), T5(A)
Fruit and Vegetable Screener: self-report of fruit and vegetable consumption.	T1(A), T3(A), T4(A), T5(A)
Physical Activity Screener: self-report of physical activity.	T1(A), T3 (A), T4(A),T5(A)
Sexual Risk: self-report of sexual activity, birth control, and condom use.	T1(A), T3(A), T4(A), T5(A)
Patient Health Questionnaire-9 (PHQ-9): self-report of DSM-V symptoms for depression.	T1(A), T3(A), T4(A), T5(A)
Safety: self-report to assess behaviors that contribute to unintentional injuries (e.g., seat belt use, helmet use).	T1(A), T3(A), T4(A), T5(A)

Key: T1 = Timepoint 1 (Baseline) T4 = Timepoint 4 (6 month)
T2 = Timepoint 2 (1-day) T5 = Timepoint 5 (1 year)
T3 = Timepoint 3 (3-month)
A = Adolescent survey
C = Caregiver survey *See Table 2 for Individual Health Risk Outcomes and Summary Risk Variable

Table 2: Summary Risk Variable and Individual Health Risk Outcomes

TOPIC AREA	Original variable	Summary Health Risk Variable	Dichotomized Individualized Health Risk Variable (Risk vs. no risk)
EATING			
Sweetened beverage consumption	0, 1, 2, 3+	# of sweetened beverages consumed in a typical day	2-3+ vs 0-1
Fruit and vegetable consumption	0-5+	# of fruits and vegetables consumed in a typical day	0-3 vs. 4+/day
ACTIVITIES			

Physical activity (60+ minutes)	0-7	# of days with >60 minutes of physical activity in an average week	0-3 days/week vs. 4-7 days/week
Sleep	0-12+	# of hours of sleep on a typical night	0-7 hours vs. 8+ hours
SAFETY			
Seatbelt Use	4 pt. scale	Frequency of seatbelt use in a car	Not always vs. always
Helmet Use	4 pt. scale	Frequency of helmet use when bicycling	Not always vs. always
DUI/Riding with a DUI driver	Dichotomous	Yes vs. no	Yes vs. no
Texting while driving	4 pt. scale	Frequency of texting while driving (4-point scale)	NOT INCLUDED IN SUMMARY RISK VARIABLE
ALCOHOL AND DRUGS			
Drinking frequency	0-30	Decrease in # of days on continuous scale	≥1 (Ages 13-15) vs. 0 ≥2 (Ages 16-17) vs. 0-1 ≥3 (Age 18) vs. 0-2
Drinking quantity (typical or maximum)	0-15+	# of alcoholic drinks typically consumed per occasion	≥3 (Girls 13-17 and Boys 13) vs. 1-2 ≥4 (Girls 18 and Boys 14-15) vs. 0-3 ≥5 (Boys 16-18) vs. 0-4
Marijuana use frequency	0-30 days and/or 0-365 days	#of days used marijuana in the past 30 days and or year	≥1 days/month (Ages 13-15) vs. 0 ≥2 days/month (Ages 16-18) vs. 1 ≥1 days/year(Ages 13-15) vs. 0 ≥6 days/year (Ages 16-18) vs. 0-5
SEXUAL ACTIVITY			

Condom Use	4 point scale	Frequency of condom use with sexual intercourse	Not always vs. always (or not sexually active)
Birth control use	Dichotomous	Use of any birth control at last sexual intercourse (yes/no)	Not always vs. always (or not sexually active)
EMOTIONS			
Depression (PHQ-9)	0-27	Score on PHQ-9	Total score on PHQ 10 or higher vs. 0-9

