For *Aim 2*, analyses will be based on patient survey responses to the 8-item satisfaction scale, patient perception of PCP communication, and the summary health risk variable, which will all be treated as continuous response variables. The summary health risk variable constructed from a count of dichotomized key risk behaviors (as shown in Table 2). First, satisfaction levels and risk behaviors will be summarized for each period (pre- and post-intervention) and will be compared using two sample t-tests. For the main analysis, we will apply mixed effects models similar to those proposed in Aim 1 to examine the intervention effect. For patient satisfaction, PCP satisfaction, adolescent's perception of PCP communication and health risk behaviors, the analysis will be cross-sectional comparisons at one day following the primary care visit. Let Y_{ij} denotes the satisfaction at one-day post visit of adolescent j within PCP i , let X_{ij} denote whether the PCP has received intervention at the time of visit, then the following mixed effects model can be applied

$$Y_{ij} = \mu + \alpha X_{ij} + b_i + \varphi \text{Covariates} + \varepsilon_{ij},$$

where b_i accounts for within-PCP correlations for adolescents seen by the same PCP. The fixed effect α captures the intervention effect on the patient satisfaction. Similar model can be applied to PCP outcomes and we can account for within-clinic correlations as well.

When examining the intervention effects on adolescents individual risky behaviors (alcohol use, marijuana use, unprotected sexual activity, depression, physical activity, healthy food consumption, seatbelt and helmet use) at baseline, 3, 6, and 12 months after the primary care visit, same modeling framework as outlined for Aim 1 can be applied.

3.3.3 Heterogeneity of Treatment Effects.

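### Table 2 leaves zero out of both categories for drinking quantity (girls 13-17, boys 13) and for monthly marijuana days (ages 16-18)

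*Combined protocol and SAP*

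**What the plan says.** Table 2 (section 3.2) gives, for each health risk item, the range of the underlying variable, a form for the summary variable, and a binary risk versus no-risk split.

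- **Drinking quantity**, recorded from 0 to 15 or more, has three splits by sex and age: "≥3 (Girls 13-17 and Boys 13) vs. 1-2", "≥4 (Girls 18 and Boys 14-15) vs. 0-3" and "≥5 (Boys 16-18) vs. 0-4".
- **Drinking frequency**, recorded from 0 to 30 days, is split as "≥1 (Ages 13-15) vs. 0 ≥2 (Ages 16-17) vs. 0-1 ≥3 (Age 18) vs. 0-2".
- **Marijuana days per month**, recorded from 0 to 30, is split as "≥1 days/month (Ages 13-15) vs. 0" for the younger group and "≥2 days/month (Ages 16-18) vs. 1" for the older group. The yearly splits put 0 in the no-risk category at all ages.
- **Helmet use** is described as "Frequency of helmet use when bicycling" on a four-point scale, divided into always and anything less. No rule is given for those who do not cycle. The condom and birth-control rows do state that adolescents who are not sexually active belong in the no-risk category.

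For Aim 2, section 3.3.2 says: "The summary health risk variable constructed from a count of dichotomized key risk behaviors", with a pointer to Table 2. No other section supplies a coding rule for these cases.

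**The concern.** These splits define outcomes. Table 1 lists the health risk items among the main outcomes, and the Aim 2 summary variable is built from the binary versions.

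Where zero belongs to neither category, the best possible result has no code. A 16-year-old who goes from 2 marijuana days a month to 1 moves from risk to no risk; one who goes from 2 to 0 cannot be placed. The items are measured again at 3, 6 and 12 months, so dropping zeros would select the analysed adolescents on behaviour that the intervention is meant to change.

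The missing-data plan could add to the problem. Section 3.3.1 foresees multiple imputation and inverse probability weighting. If uncoded zeros were treated as missing, abstainers in the affected groups would be imputed or weighted for, although their answer is known.

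**Working it through.** The plan gives no figure to reproduce here. The check is whether each allowed value of each item falls in a category, in each of the 12 sex-by-age cells (girls and boys, single years 13 to 18).

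**Step 1. Enumerate the values.**

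| Item | Range | Groups where 0 has no category | Cells with a gap |
|---|---|---|---|
| Drinking frequency | 0-30 | none | 0 of 12 |
| Drinking quantity | 0-15+ | girls 13-17, boys 13 | 5 + 1 = 6 of 12 |
| Marijuana, days/month | 0-30 | girls and boys 16-18 | 3 + 3 = 6 of 12 |
| Marijuana, days/year | 0-365 | none | 0 of 12 |

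Zero is the only unassigned value. Both gaps occur in 2 cells (girls 16 and 17). At least one occurs in 6 + 6 − 2 = 10 of 12 cells, all except boys 14 and 15.

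**Step 2. Size of the groups.** Section 2.1 plans about 300 adolescents, and the section on gender of subjects expects 150 girls and 150 boys. The documents give no age distribution. Assume ages are evenly spread: 150 / 6 = 25 adolescents per cell.

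- Drinking-quantity gap: 6 × 25 = 150 of 300.
- Monthly marijuana gap: 6 × 25 = 150 of 300.
- At least one gap: 10 × 25 = 250 of 300 (83%).

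**Step 3. Adolescents actually uncoded.** These are the members of the affected groups who report 0. The documents give no prevalence, so the possible range is 0 to 150 per item. As an illustration only, assumed non-use of 70% to 90% gives 0.70 × 150 = 105 to 0.90 × 150 = 135 per item.

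**Step 4. Effect on the summary count.** Two readings are open.

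- The count adds 1 for each risk threshold met. Zero drinks is below 3 and zero days is below 2, so the abstainer adds 0 and the count is unaffected.
- An uncoded item is set to missing. The count is then missing or imputed for every abstainer in the affected groups.

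**Step 5. Check the repair.** With no-risk categories of 0-2 drinks and 0-1 days per month, no value is left unassigned in any of the 12 cells.

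**The case against.** The strongest reply is that these are two drafting slips with one plausible reading. The risk thresholds are explicit, the column is meant to be binary, and all the neighbouring splits put 0 with no risk. Section 3.3.2 also has variables checked and constructed before any effect is analysed, and an analysis plan put to the study team and the advisory board. A large block of uncoded zeros would probably be noticed. This stands as to the likely cause and makes a silent error less likely, but it supplies no coding rule.

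Four stronger readings are tempting, and the documents do not support them.

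- *The alcohol and marijuana analyses compare only heavier with lighter users.* Zero is coded in the other 6 of 12 cells for each faulty item, and at every age for drinking frequency and yearly marijuana days. Section 3.3.2 also does not say that the individual-behaviour models must use the binary versions; the numeric versions include zero. The sound rows do not repair the faulty ones, however. Drinking quantity has its own binary variable. Table 2 leaves the monthly and yearly marijuana measures as alternatives, and Table 1 refers to the past 30 days, which is the window with the gap.
- *The summary count is undefined for most participants.* This holds only under the second reading in step 4, and only for those who report zero.
- *83% of participants are affected.* That is the share who belong to a group with a gap, under an assumed age distribution. It is not the share left uncoded.
- *Non-cyclists have no code, or are always scored as at risk.* The four response options are not shown, so neither can be established. What can be shown is that no rule is stated.

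**Conclusion.** The point holds for two cells of Table 2, which are wrong as written: zero is unassigned for drinking quantity in girls 13-17 and boys 13, and for monthly marijuana days at ages 16-18. Applied literally, abstainers in those groups have no value on these two binary items. Harm to the summary variable is conditional on how uncoded items enter the count, which the plan leaves open.

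Each gap concerns half of the sex-by-age cells. The figure of about 150 adolescents per item rests on evenly spread ages, and the number uncoded cannot be derived from the documents. Because the cells set thresholds for named main outcomes, they should be corrected before outcomes are analysed, so that the coding is not chosen afterwards. The helmet item is a minor clarification and adds nothing to the weight of the point.

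**What to change.** In Table 2, change the no-risk category for drinking quantity in girls 13-17 and boys 13 from 1-2 to 0-2, and for monthly marijuana days at ages 16-18 from 1 to 0-1. In section 3.3.2, add a sentence stating that non-use counts as no risk in the summary variable.

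As a clarification, state how adolescents who do not cycle are coded on the helmet item, as is already done for those who are not sexually active. This requires checking whether the questionnaire offers a response for them.

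The cost is two table cells and two sentences. The alcohol and marijuana corrections need no new data, and nothing in the design or sample size changes.

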1.1. Purpose

The purpose of this study is to evaluate the perceived impact and effectiveness of our system of interventions (I-ACT with Check Yourself) among a sample of adolescents aged 13-18 drawn

from the targeted primary care clinics using a group who receives usual care as a comparison. This study has two aims:

Aim 1. To evaluate I-ACT with Check Yourself on intermediary targets: improving adolescent motivation for health, increased provision of appropriate preventive counseling, and follow-up care. We will examine the impact of I-ACT with Check Yourself on adolescent self-report of motivation for health at baseline and 3, 6 and 12 months following the primary care visit. We will also examine the impact of I-ACT with Check Yourself on the adolescent self-report of receipt of PCP-delivered risk reduction counseling at one day following the primary care visit and follow-up care at 3, 6 and 12 months following the primary care visit.

Aim 2. To evaluate the effects of I-ACT with Check Yourself on adolescent satisfaction with the provider visit, perception of patient-centeredness of care, and health risk behaviors. We will explore the impact of I-ACT with Check Yourself on health care satisfaction among adolescents and caregivers at one day following the primary care visit. We will also explore the impact of I-ACT with Check Yourself on adolescent self-report of their perception of patient-centeredness of care at one day following the primary care visit. We will examine the effect of I-ACT with Check Yourself on producing significantly lower rates of alcohol use, marijuana use, unprotected sexual activity, and depression compared to a usual care group at baseline and 3, 6, and 12 months after the primary care visit. We will also examine the effect of I-ACT with Check Yourself on producing significantly higher levels of physical activity, fruit and vegetable consumption, and seatbelt and helmet use when compared to a control group at baseline and 3, 6 and 12 months after the primary care visit.

2. Criteria for Subject Selection

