in which Y_{ijk} denotes the health motivation reported by j th patient within i th provider at k th time interval, X_{ijk} is a binary indicator of exposure to the intervention for the provider and the predictor of interest, T_k is a binary indicator of the k th assessment, b_i and b_{ij} are PCP and adolescent specific random effects that account for the within PCP and within adolescent correlations, and ε_{ijk} is the error term. Additional patient-level or PCP-level confounding variables can be adjusted in the model as well.

With this model, the fixed effects α captures the treatment effects on mean responses and time-by-intervention interaction coefficients γ_k 's captures the treatment effects across time. Fixed effects β_k 's aim to capture any temporal trend or learning effects. Using this approach, both within-adolescents and between adolescents information will be used to estimate the treatment effects. All coefficients will be tested using Wald test. Also note this

model framework is flexible enough that a patient can be enrolled at any time during the study and the model can accommodate different numbers of post-intervention assessments. For example, for an adolescent enrolled after his/her PCP has received intervention, all X_{ijk} 's would take value 1 for that subject.

We will apply linear mixed effects models for Gaussian outcome Y_{ijk} , and generalized linear mixed effects models for other types of outcomes (e.g., logistic model for binary outcome).

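### Table 2 defines the individual outcomes as risk versus no risk, but Aim 2 asks about levels of activity and of fruit and vegetable intake; the plan should make the original counts the leading analysis scale

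*Combined protocol and SAP*

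**What the plan says.** Table 1 (section 3.2) places the activity, fruit and vegetable, and PHQ-9 measures among the main outcomes, collected from adolescents at T1, T3, T4 and T5. Its footnote sends the reader to Table 2 for the individual outcomes and the summary variable.

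Table 2 gives each topic its original variable, a column headed Summary Health Risk Variable, and a column headed "Dichotomized Individualized Health Risk Variable (Risk vs. no risk"). The last column holds the cuts:

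- PHQ-9, recorded 0-27: "Total score on PHQ 10 or higher vs. 0-9".
- Physical activity, recorded 0-7: "0-3 days/week vs. 4-7 days/week".
- Fruit and vegetables, recorded 0-5+: risk is 0-3 a day, no risk is 4 or more.

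Section 3.3.2 treats three Aim 2 variables as continuous: satisfaction, perceived PCP communication and the summary variable. Of the last it says: "The summary health risk variable constructed from a count of dichotomized key risk behaviors (as shown in Table 2"). For the individual behaviours, at baseline and 3, 6 and 12 months, it says only that the "same modeling framework as outlined for Aim 1 can be applied". On model type, the Aim 1 text reads "We will apply linear mixed effects models for Gaussian outcome", with generalized linear mixed models for other outcomes and logistic regression as the example for binary ones.

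Aim 2 (section 1.1) uses two kinds of language. It looks for "significantly lower rates of alcohol use, marijuana use, unprotected sexual activity, and depression compared to a usual care group", and for "producing significantly higher levels of physical activity, fruit and vegetable consumption".

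**The concern.** For activity and diet, Aim 2 asks how much adolescents do or eat. The share above a cut is a different quantity. With activity split between 3 and 4 days, an adolescent who goes from 0 to 3 days is recorded as unchanged, while one who goes from 3 to 4 is recorded as a full success. A change in PHQ-9 from 20 to 11 also disappears.

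The second cost is precision. The full scores and counts are collected at every relevant visit, and section 3.3.1 calls statistical power a key consideration. Reducing a count to two categories when the count is already in hand works against that. If the scale is left open instead, it could be chosen after the data are seen, for several named main outcomes.

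**Working it through.** **1. The plan's own figure.** Section 3.1 expects about 30% of roughly 1000 invited dyads to take part: 1000 × 0.30 = 300, which matches section 2.1. This is recruitment arithmetic. Section 3.3.1 mentions sample size calculations but does not show them. The documents give no alpha, power, effect size, SD, intraclass correlation or expected share at risk, so there is no power figure to reproduce.

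**2. Which scale does the text specify?**

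- For the dichotomies: the only Table 2 column labelled as individual is the dichotomised one, and the list of continuous responses in section 3.3.2 omits the individual behaviours.
- Against: Table 2 also describes scores and counts, but under the summary heading. Section 3.3.2 builds the summary from the dichotomies, so the table heading and the analysis text conflict.
- Neither place names the analysis scale for each individual outcome.

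**3. Normal-theory loss.** For a small location shift in a normal score, with share p beyond the cut, the efficiency of the dichotomy relative to the mean is φ(z_p)² / [p(1 − p)], and the loss is 1 minus that. The values of p are assumptions. The last column is 300 × efficiency.

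| Assumed p | Efficiency | Loss | Equivalent of 300 |
|---|---|---|---|
| 50% | 0.637 | 36.3% | 191 |
| 30% | 0.576 | 42.4% | 173 |
| 20% | 0.490 | 51.0% | 147 |
| 10% | 0.342 | 65.8% | 103 |

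Suppose an effect had 80% power on the score (two-sided 0.05; an illustrative starting point, not a figure from the plan). Power after dichotomising is Φ(2.802 × √efficiency − 1.96): 0.61 at p = 50%, 0.50 at 20% and 0.37 at 10%.

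**4. Check with a finite shift.** Assume a shift of 0.3 SD, 80% power and no clustering. On the score, n per arm = 2 × 2.802² / 0.3² = 175 after rounding up. On the dichotomy, the share beyond the cut falls from p to Φ(−(z_{1−p} + 0.3)). The usual two-proportion formula (pooled variance under the null) then gives 278 per arm at p = 50% (falling to 38.2%), 400 at 20% (to 12.7%) and 609 at 10% (to 5.7%). For p below 50%, the numbers would be smaller if the smaller group grew.

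**5. Check on the recorded scales.** These are not normal scores, so the efficiency was recomputed as the squared derivative of the proportion over p(1 − p), divided by the squared derivative of the mean score over its variance. Activity and diet used a latent normal rounded to the recorded categories. PHQ-9 used a negative binomial capped at 27, with a proportional change in the mean. All means, SDs and dispersions are assumptions.

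| Outcome | Assumed range | Share at or above the cut | Loss |
|---|---|---|---|
| Fruit and vegetables, 0-5+ | mean 2-3.5, SD 1.3-1.8 | 12-50% | 29-59% |
| Activity, 0-7 days | mean 3-5, SD 1.8-2.2 | 39-80% | 33-47% |
| PHQ-9, 0-27 | mean 3-6, dispersion 0.8-2 | 3-22% | 33-68% |

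Steps 3 to 5 ignore clustering and the stepped-wedge structure. The ratios carry over only if both affect the two scales equally.

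**The case against.** The strongest reply is that the plan may already analyse the scores. The Aim 1 framework allows linear models, and no sentence assigns logistic models to these outcomes. The dichotomies have a stated use, as components of the summary count, and raw days, servings and PHQ points could not form such a count. The texting row fits this: the note excluding it from the summary sits in the dichotomised column. The drinking-frequency row mentions a continuous scale in the other column. One could conclude that the two headings were interchanged.

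Part of this stands. A reader might infer that the plan commits to binary-only logistic analyses; the text does not go that far. But an interchange of headings does not settle the matter: the word dichotomised correctly describes the cells beneath it, and the list of continuous responses would still omit the individual behaviours.

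Three further objections stand in full. Aim 2 asks about rates of depression, so the PHQ-9 proportion answers the question asked. The loss figures rest on assumed distributions. And adjusting for the T1 value conflicts with section 3.3.2 if T1 also remains among the modelled responses.

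**Conclusion.** The point holds for activity days and fruit and vegetable servings. Read literally, the plan gives these as risk versus no risk while Aim 2 asks about levels, and the table and analysis text disagree on which column serves which analysis. If only the dichotomies are analysed, the loss of information is material: 36-66% under normality with 10-50% beyond the cut, and about 30% to two thirds on the assumed bounded or skewed scales.

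A reader might infer three stronger conclusions that the documents do not support:

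- That 36-66% is the loss in this trial. No prevalence, mean or SD is given, so it is an illustration.
- That the PHQ-9 cut fails Aim 2. It matches the rate question; the remaining argument is that the total score is more sensitive.
- That the trial has no power to spare. The sample size calculations are not shown, so this cannot be judged.

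This is a correctable loss of relevance and precision on named main outcomes, not a fatal fault.

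**What to change.** In section 3.3.2, name the analysis scale of every individual outcome before outcome data are examined. The analysis plan that section promises to present to the study team and advisory board is a natural place.

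- **Activity days and fruit and vegetable servings:** make the original scale the leading analysis, using the mixed models already described: linear where approximately Gaussian, otherwise a suitable generalized or ordinal model. The 0-5+ item is top-coded, so its fit needs checking.
- **Table 2 dichotomies:** keep them as supportive results and as components of the summary count.
- **PHQ-9:** keep the proportion at 10 or higher for the rate question, and add the total score as a more sensitive analysis.
- **Baseline:** if the T1 value is a covariate, remove T1 from the response vector.
- **Table 2 headings:** correct them to agree with section 3.3.2.

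No new data are needed; the change is to wording. The downside is that, where the linear model is used, the leading activity and diet estimates become mean differences, which some readers find harder to interpret than a risk proportion. Reporting the proportions alongside meets that.
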